6.2.2.3 Sensitivity analyses of secondary efficacy variables

Sensitivity analyses of secondary variables will be performed in the FAS the same way as for primary efficacy variable. If the baseline values of secondary endpoints are missing, then only multiple imputation will be applied for those subjects. Please see the details in Section 6.2.1.4.

6.2.3 Exploratory efficacy variables and analyses

Exploratory efficacy variables include:

- Echocardiographic parameters, as described in Section 9.4.3 of Clinical Study Protocol, measured values and absolute / relative change from baseline at 20 weeks
- Mandatory biomarkers, as described in Section 9.4.4 of Clinical Study Protocol, measured values and absolute / relative change from baseline at 20 weeks, including UACR, cystatin-C, NGAL for the evaluation of kidney function
- Time from randomization to CV mortality, HF hospitalization and urgent visits for HF as clinical outcomes (both separate and composite outcomes)
- Time from randomization to all-cause mortality, non-fatal myocardial infarction, non-fatal stroke
- EQ-5D-5L QoL, as described in Section 9.4.6.2 of Clinical Study Protocol, measured values and absolute / relative change from baseline
- KCCQ (Appendix 9.3; excluding symptom stability domain and self-efficacy domain), measured values, absolute change and relative change from baseline
- Change in NYHA class
- Absolute change in score on Borg CR 10 Scale

Time to adjudicated clinical outcome events since randomization (both separate and composite outcomes) will be described by means of Kaplan-Meier estimates by visit in FAS. The subjects who do not have the corresponding clinical outcomes until week 26 (planned Visit 9, upper time limit, i.e. $182+7=189$ days) will be considered as right-censored at the minimum of date of last visit, date of Visit 9, and date of death (in case death is non CV death). KM estimates will be presented by individual treatment groups and by all neladenoson groups pooled as well as 5 mg and 10 mg doses pooled as low dose, 20 mg, 30 mg, 40 mg doses pooled as high dose versus placebo.

Additionally time to adjudicated on-treatment clinical outcome events since randomization (using both separate and composite outcomes) will also be described by means KM estimates

Statistical Analysis Plan

by visit. The subjects who don't have the corresponding clinical outcomes 6 weeks after last dose will be considered right censored at minimum of date of last visit, 6 weeks after last dose and date of death (in case death is non CV death). KM estimates will be presented by individual treatment groups and by all neladenoson groups pooled as well as 5 mg and 10 mg doses pooled as low dose, 20 mg, 30 mg, 40 mg doses pooled as high dose versus placebo.

All-cause mortality, non-fatal myocardial infarction, non-fatal stroke will be analyzed descriptively in FAS, providing incidences. Proportions of responses to single KCCQ questions will be given by visit. The 5 individual domain scores and 3 summary scores of the KCCQ and their changes to baseline (both absolute and relative change) will be summarized by visit. For scoring see Appendix 9.3.

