6.4 Withdrawal of patients from study

6.4.1 Withdrawal

An excessive rate of withdrawals (either patients discontinuing study medication or study withdrawal) can render the study non-interpretable. Therefore, un-necessary withdrawal of patients should be avoided and all efforts should be taken to motivate patients to comply with all the study specific procedures and to be followed until the end of the trial to detect the occurrence of cardiovascular events / assess vital status.

Before permanently discontinuing study medication (either initiated by the patient or the investigator) an interruption should be considered. Patients, who have temporarily discontinued study medication for any reason, should restart as soon as medically justified in

14 FEB 2017 Version: 1.0 Page: 27 of 85

the opinion of the investigator; the patient can re-start at any time before the end of treatment (EOT) visit. In addition, patients should not be withdrawn from the study drug or from the study solely for reaching a potential cardiovascular event.

All patients who permanently discontinue study medication should come in for the EOT / premature discontinuation visit as soon as possible after discontinuation of the study medication and the safety follow-up visit 4 weeks after the last dose. In addition, they will be contacted by the investigator via the scheduled Week 26 phone call to assess occurrence of cardiovascular events.

The investigator should show due diligence and explore all possible options to reach a patient who fails to return to a visit. The site must document all attempts to try to contact the patient in the medical records / source documents.

In order to avoid loss-to-follow-up, the investigator should ask the patient at the study start for the contact details of a relative or friend who can be contacted in case the patient cannot be reached.

Patients should not be withdrawn from follow-up unless the patient explicitly withdraws consent to be contacted. All efforts should therefore be made to minimize the number of patients who withdraw such consent as, in general, no further information on cardiovascular events and survival status may be collected after that point.

Withdrawal criteria

Patients *must* be withdrawn from the study if any of the following occurs:

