11.4 Missing data

The following measures will be implemented to minimize the amount of missing data.

- Encourage further participation in the study, i.e. phone call 26 weeks after the start of treatment, even if the study medication is discontinued early.
- If the patient does not attend the visits in person, the investigator should make every effort to collect information on mortality and / or hospitalization from other sources, e.g. family / friend / general physician / etc.
- Ask sites to call patients the day before certain study visits to remind them to remember
 the time they take their study medication and to remind them in case study medication
 should not be taken at home the next day.
- Educate patients on the AVIVO device and train sites to prepare the patient's skin for adherence of the sensor. Ask sites to call patients at the end of the wearing period to provide instructions for removal, storage and return at the next visit.
- Try to avoid unnecessary patient withdrawals (see Section 6.4).

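### The clinical-outcome Kaplan-Meier rule censors event-free patients at their last visit but counts events after it, a small upward bias in an exploratory analysis

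*SAP*

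**What the plan says.** SAP 6.2.3 describes time from randomization to adjudicated outcomes (CV death, HF hospitalization, urgent HF visit, separately and combined) by Kaplan-Meier estimates. The censoring rule covers "The subjects who do not have the corresponding clinical outcomes until week 26", where Week 26 is given an "upper time limit, i.e. $182+7=189$ days". Those patients "will be considered as right-censored at the minimum of date of last visit, date of Visit 9, and date of death", and the death date applies only "in case death is non CV death". An outcome by Day 189 is an event whatever the date of the last visit.

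The on-treatment version has the same structure. Patients without an outcome "will be considered right censored at minimum of date of last visit, 6 weeks after last dose and date of death", again for non-CV death only.

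The protocol seeks outcome information beyond attended visits. Section 6.4.1 wants patients "to be followed until the end of the trial to detect the occurrence of cardiovascular events / assess vital status". Section 11.4 says that when a patient does not attend, "the investigator should make every effort to collect information on mortality and / or hospitalization from other sources". Section 9.4.5.1 obliges investigators to report all suspected endpoints, without tying this to a visit.

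Neither document defines the date of last visit for this rule. For time to end of study, SAP 4.3 uses the last visit only when the patient leaves the study early. SAP 6.2.3 has no such limit.

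**The concern.** Two things go wrong if the minimum is applied as written.

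- **The death term is close to inert.** A last visit normally precedes death, so inside a minimum the death date can bind only on a same-day tie or if a contact is dated after the death.
- **Follow-up after the last visit is used one-sidedly.** Suppose a patient has no Visit 9 contact but the site learns the outcome status elsewhere. If there was an event, the patient stays in the risk set until that event. If there was none, the patient leaves the risk set at the last visit. Censoring then depends on the outcome, which the Kaplan-Meier estimator does not allow, and the estimated risk is too high.

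The curves are planned by dose group and for pooled low and high doses against placebo. Protocol section 4 says that the totality of the data, exploratory endpoints included, informs the benefit/risk assessment and the phase III decision.

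**Working it through.** **The plan's own figure.** Visit 9 is at Week 26 with a window of +7 days: 26 × 7 + 7 = 189 days. This matches the SAP.

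**The rule applied to single patients (HF hospitalization curve).**

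| Patient | SAP rule | Follow-up actually known |
|---|---|---|
| Last visit Day 56, non-CV death Day 80 | min(56, 80) = Day 56, censored | Day 80 (24 days lost) |
| Last visit Day 56, no Visit 9, known alive and not hospitalized to Day 182 | Day 56, censored | Day 182 (126 days lost) |
| Same, but HF hospitalization on Day 120 | Day 120, event | Day 120 |
| Stops drug early, Visit 9 call on Day 184 | Day 184, censored | Day 184 |

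Rows 2 and 3 show the asymmetry. Row 4 shows why Visit 9 completers lose nothing: Protocol 9.2.10 keeps the Week 26 call for patients who stop drug early.

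**Time lost per non-CV death.** Take deaths spread evenly over 182 days and contacts at Days 0, 14, 28, 56, 84, 140, 168 and 182. The mean gap from last contact to death is Σ(gap²) / (2 × 182) = 6076 / 364 = 16.7 days.

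**Expected inflation by hand.** Let q be the share of patients who stop attending, have no Visit 9 contact and have known status. If stopping times are even over 182 days, each such patient loses on average 91 + 16.7 = 107.7 days, or 107.7 / 182 = 0.592 of the period. Event counts do not change, so the rate is inflated by about 1 / (1 − 0.592q):

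- q = 5%: 1 / 0.970 = 1.031
- q = 10%: 1 / 0.941 = 1.063

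**Simulation.** Each setting has 400,000 patients, constant hazards, 1% non-CV death and risk read at Day 182. The documents give no event rate, non-CV death rate or value of q, so all three are assumptions. Ratios are from unrounded values.

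| Assumed risk | q | SAP rule | Censored at last known date | Ratio |
|---|---|---|---|---|
| 5% | 0 | 5.02% | 5.02% | 1.001 |
| 5% | 5% | 5.17% | 5.01% | 1.030 |
| 5% | 10% | 5.24% | 4.93% | 1.062 |
| 10% | 0 | 9.95% | 9.94% | 1.001 |
| 10% | 5% | 10.36% | 10.07% | 1.029 |
| 10% | 10% | 10.61% | 10.02% | 1.059 |

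At a 10% risk the bias is 10.36 − 10.07 = 0.29 point and 10.61 − 10.02 = 0.59 point. With q = 0 and non-CV mortality raised to 5%, the ratio is still only 1.004-1.005.

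**Scale against sampling error.** At a 10% risk the binomial standard error is √(0.1 × 0.9 / 72) = 3.5 points for placebo. For the 20, 30 and 40 mg pool (3 × 48 = 144 patients) it is √(0.1 × 0.9 / 144) = 2.5 points.

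**The case against.** The strongest reply is that few patients can be affected.

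- Visit 9 is a numbered visit held by phone, and it is kept after early drug discontinuation.
- Patients who withdraw consent to contact generally yield no later information (Protocol 6.4.1). Their later events and later event-free time are both unseen, and censoring at the last visit is then ordinary practice.
- Protocol 11.4 asks for every effort, not a guaranteed result, and only on mortality and hospitalization. A relative's report that the patient is alive and was not admitted does not rule out an urgent HF visit. For that outcome and the composite, stopping at the last direct contact is defensible, provided later events are not counted either.
- The on-treatment curve is less exposed. For an on-schedule completer, six weeks after last dose falls at about Day 139 + 42 = 181, just before Visit 9. For early stoppers reached at Week 26 it normally precedes the last contact. In both cases it binds correctly.
- The section specifies no test or hazard ratio, and the tabulated deaths and the incidences of all-cause mortality, myocardial infarction and stroke do not depend on this rule.

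All of this stands and limits the point to a small group and a small effect. It does not make the rule correct for that group. The wording in SAP 4.3 suggests that SAP 6.2.3 has a drafting gap, but a programmer would implement the text as written.

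**Conclusion.** The rule is wrong as written, with a small effect. If 5-10% of patients miss Visit 9 with known status, the Kaplan-Meier risk is overstated by about 3-6% in relative terms, roughly 0.3-0.6 point at a 10% risk. The non-CV-death part alone is negligible. These sizes rest on assumed event rates and shares. The primary test, type I error and sample size are not affected.

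Three stronger conclusions might be inferred, and the documents do not support them.

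- **A large bias.** A share of 25% would give about 17%. The only 25% available is the expected shortfall of complete per-protocol data in Protocol 10.4, which is not a rate of missed Visit 9 calls with known status.
- **A false excess risk on drug.** Shares of 5% on placebo and 25% on high dose would produce an apparent risk ratio of about 1.14. Nothing in the documents indicates such a contrast between arms.
- **A collapsed curve.** If the last visit meant the last site visit, completers would be censored by about Day 168 while later events still counted, and the curve would be uninterpretable after that. The protocol numbers the Week 26 call as Visit 9, so this is not the natural reading, but the undefined term should be settled.

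**What to change.** In SAP 6.2.3:

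1. State that the date of last visit includes the Visit 9 call and any later documented contact.
2. Censor patients without the outcome at the earliest of Day 189, the date of non-CV death, and the last date documented free of the specific outcome analysed. A death report counts as follow-up to the date of death.
3. For outcomes that outside sources cannot rule out, namely urgent HF visits and the composite, use the last direct contact with the patient and do not count events after it. The exception is patients who die, who are followed to death.
4. Apply the same rule to the on-treatment analysis, with six weeks after last dose as a further limit.

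The exception in item 3 leaves a trace of the asymmetry when a patient already out of contact dies of a CV cause. The number of such deaths should be reported beside the curve.

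The cost is a few sentences across two SAP paragraphs, with no extra patients or procedures. The downside is that a last-known-event-free date must be recorded for the few patients followed through other sources. The protocol sections cited ask sites for the information but not explicitly for that date.

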6.3 Safety

The summaries of the safety data will be completed for the safety analysis population (SAF). No formal statistical test will be performed for the safety variables.

6.3.1 Extent of exposure

Study medication will be summarized for the safety population by treatment group, using descriptive statistics such as frequency and proportion (for categorical variables), mean, median, and standard deviation (for continuous variables).

The treatment duration (date of last study medication- date of first study medication+1) will be summarized descriptively. Additionally the number of subjects by treatment duration category will be given (≤ 28 days, $>28-\leq 56$ days, $>56-\leq 84$ days, $>84-\leq 140$ days).

The time on study medication (treatment duration excluding days off study medication) will be calculated and summarized descriptively.

The number of tablets taken will be summarized descriptively, as well as corresponding extent of exposure (total amount of intake in mg).

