9.2.2 Visit 2 (Week 0, baseline)

At Visit 2 eligibility must be re-assessed before the patient is randomized to a treatment arm. Please note: laboratory eligibility criteria are based upon local historical records, not central laboratory findings. Even retrospectively, central laboratory results from the baseline visit will not render a patient ineligible for the study. If a patient is not eligible for randomization, or withdraws for other reasons before randomization, he / she will be considered a screening failure even though the visit is not named a screening visit (for details see Section 6.4.1).

The following procedures will be performed **before randomization**:

- Review in/exclusion criteria and confirm patient eligibility
- Quality of life questionnaires (KCCQ and EQ-5D-5L), to be completed by the patient (Section 9.4.6)
- Medical and surgical history collection and recording (Section 9.3.2)
- Tobacco smoking and alcohol history collection and recording
- Assessment of caffeine-containing beverage and chocolate consumption during the previous 4 weeks
- Physical examination (Section 9.6.3.2)
- Weight and height measurement (BMI will be calculated automatically)
- 12-lead ECG (Section 9.6.3.3)
- NYHA class assessment (Section 9.4.5.2)
- Blood pressure and heart rate measurement (Section 9.6.3.4)
- Adverse events assessment (Section 9.6.1.3)
- Concomitant medication collection and recording (Section 8.1)
- 6MWD test (Section 9.4.1)

14 FEB 2017 Version: 1.0 Page: 37 of 85

- Borg CR 10 Scale (Section 9.4.2)
- Collection of AVIVO device applied at Visit 1 (Week -1)
- Echocardiography (Section 9.4.3)
- AVIVO device application, worn for 7 days (Section 9.6.3.5)

After all above procedures are done, the patient can be randomized via IxRS (Section 7.3).

The following procedures should be performed after randomization and before study medication intake:

- Blood sampling for safety (Section 9.6.3.1).
- Blood and urine sampling for biomarkers (Section 9.4.4)
- Study drug dispensing (Section 7.7)

The following procedures should be performed during and after study medication intake:

- Start of study medication (Section 7.1). The first dose of study medication will be taken after all previous procedures are completed; the time of intake should be recorded. The patients will be instructed to remember the time of medication intake as precisely as possible on selected days.

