9.2.8 Visit 7 (Week 20, EOT or premature discontinuation)

The last dose of study drug should be taken the day before the visit. The patients should remember the time of the last dose as precisely as possible; this information will be recorded in the patient's file. It is recommended to make a reminder phone call to the patients on the previous day.

If a patient discontinues study treatment prematurely this visit should be completed as soon as possible after the last dose.

14 FEB 2017 Version: 1.0 Page: 40 of 85

- Quality of life questionnaires (KCCQ and EQ-5D-5L), to be completed by the patient (Section 9.4.6)
- Physical examination (Section 9.6.3.2)
- Weight measurement
- Assessment of caffeine-containing beverage and chocolate consumption during the previous 4 weeks
- 12-lead ECG (Section 9.6.3.3)
- NYHA class assessment (Section 9.4.5.2)
- Blood pressure and heart rate measurement (Section 9.6.3.4)
- Adverse events assessment (Section 9.6.1.3)
- Concomitant medication collection and recording (Section 8.1)
- 6MWD test (Section 9.4.1)
- Borg CR 10 Scale (Section 9.4.2)
- Collection of AVIVO device applied at Week 19
- Echocardiography (Section 9.4.3)
- Blood sampling for safety (Section 9.6.3.1).
- PK sampling one day after the last dose (Section 9.4.6.2).
- Blood and urine sampling for biomarkers (Section 9.4.4)
- Unused study drug collection (Section 7.7)

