Page: 8 of 38

1. Introduction

This statistical analysis plan (SAP) describes the study objectives, study design, study population, efficacy and safety variables, statistical analysis methods, and study tables to be used in this study. It is based on the original protocol, Version 1.0, dated 14 FEB 2017.

2. Study Objectives

[figure not shown]
The objective of the study is to find the optimal dose of neladenoson bialanate for the Phase III trial by detecting and characterizing a significant dose-response relationship in the primary efficacy endpoint, absolute change from baseline in 6-minute walking distance (6MWD) at 20 weeks, in patients with chronic heart failure with preserved ejection fraction (HFpEF), and by characterizing the safety, tolerability and pharmacodynamic effects of the compound when given in addition to appropriate therapy for specific co-morbidities.

An exploratory objective is to further assess pharmacokinetic parameters and blood and urine biomarkers.

3. Study Design

Study 17582 is a multicenter, randomized, placebo-controlled, parallel group, double blind, dose-finding Phase II study. [Figure 3-1](#) displays the overall study design.

Figure 3-1: Study design overview

Abbreviations: CV = cardiovascular; ICF = informed consent form; W = week

Approximately 288 patients from approximately 90 study centers worldwide will be randomized to one of the active treatment dose arms or placebo, in addition to their background therapy.

Statistical Analysis Plan

Protocol No.: < BAY 1067197/17582 >

Page: 9 of 38

The study will comprise a 1-week run-in period, 20-week treatment period, and a 6-week follow-up period (27 weeks total).

Patients will have site visits at Weeks -1, 0 (baseline), 4, 8, 12, 20 (end of treatment visit) and 24 (safety follow-up visit). In addition, 2 phone calls at Weeks 2 and 26 will be made to assess patients' safety, and one additional phone call – to remind the patients of AVIVO self-application at Week 19.

6MWD test (including Borg CR 10 Scale) will be done during the run-in, to familiarize patients with the test, and at baseline, Week 8 and end of treatment / premature discontinuation visits. Safety will be monitored throughout the study. PK samples will be taken from all patients at dedicated time points. Biomarkers reflecting the pharmacodynamic activity of the drug will be examined, as well as candidate biomarkers that may predict drug response.

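### The top treatment-duration category in SAP 6.3.1 stops at 140 days, so protocol-compliant completers with 141 or 142 days of treatment fall in no category

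*SAP*

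**What the plan says.** SAP section 6.3.1 defines the quantity: "The treatment duration (date of last study medication- date of first study medication+1) will be summarized descriptively". It then adds a frequency table: "Additionally the number of subjects by treatment duration category will be given". Four bands follow: up to 28 days, over 28 to 56, over 56 to 84, and over 84 to 140. The list closes there, and no rule is given for a longer duration.

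Three protocol provisions determine how long a compliant completer is treated:

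- **First dose.** It is taken at the baseline visit (section 9.2.2): "The first dose of study medication will be taken after all previous procedures are completed".
- **Week 20 visit.** Table 9-1 sets it at Day 140 with a tolerance of 2 days either way.
- **Last dose.** Section 9.2.8 says: "The last dose of study drug should be taken the day before the visit".

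SAP section 3 describes a "20-week treatment period", which is 20 × 7 = 140 days.

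**The concern.** The upper limit of the last band equals the nominal treatment length, while the protocol lets the final visit, and with it the last dose, fall up to two days later. A patient who does everything the protocol asks can therefore exceed the limit. Followed literally, the table has no place for that patient. The patients left out would be fully exposed ones, and the rows within a dose arm would not have to sum to the number in the safety set.

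The SAP does allow for a visit window elsewhere. Section 6.2.3 sets the upper time limit for the clinical outcome events at 182 + 7 = 189 days. Section 6.3.1 uses the nominal 140 days without the corresponding 2. This looks like an oversight rather than a choice.

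**Working it through.** **Inputs**

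- Duration = last dose date - first dose date + 1 (SAP 6.3.1).
- Top band: over 84 days, up to and including 140 days (SAP 6.3.1).
- First dose: at the baseline visit, taken as Day 0 (Protocol 9.2.2 and Table 9-1).
- Week 20 visit: Day 138 to Day 142 (Protocol Table 9-1, Day 140 ± 2).
- Last dose: visit day minus 1 (Protocol 9.2.8).

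**Reproducing the SAP's own limit.** A visit on Day 140 means a last dose on Day 139. Duration = 139 - 0 + 1 = 140 days = 20 × 7. This is exactly the upper limit of the last band. The +1 in the formula cancels the day between last dose and visit, so with first dose on Day 0 the duration equals the visit day.

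**All in-window visit days, first dose on Day 0**

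| Week 20 visit | Last dose | Duration (days) | SAP category |
|---|---|---|---|
| Day 138 | Day 137 | 137 - 0 + 1 = 138 | over 84 to 140 |
| Day 139 | Day 138 | 138 - 0 + 1 = 139 | over 84 to 140 |
| Day 140 | Day 139 | 139 - 0 + 1 = 140 | over 84 to 140 |
| Day 141 | Day 140 | 140 - 0 + 1 = 141 | none |
| Day 142 | Day 141 | 141 - 0 + 1 = 142 | none |

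**Sensitivity to the day count.** Table 9-1 gives the baseline visit a window of 0 to +2 days. If study days ran from a planned Day 0 rather than from the first dose, durations would be shorter:

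- First dose on Day 1: the maximum is 141 - 1 + 1 = 141 days, still above the limit.
- First dose on Day 2: the maximum is 141 - 2 + 1 = 140 days, within the limit.

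The gap therefore remains for patients first dosed on Day 0 or Day 1. The protocol mostly times contacts from the start of treatment (sections 9.2.3, 9.2.7 and 9.2.10, and footnote a to Table 9-1), which supports counting from the first dose.

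**Other ways past the limit.** If a patient also took a dose on the visit day, against the instruction, an on-time completer would have 140 - 0 + 1 = 141 days. SAP section 4.3 replaces a completely missing stop date by the earlier of the last on-treatment visit and death. If the Week 20 visit counts as on-treatment, which the SAP does not say, an on-time completer with a missing stop date would also get 141 days.

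**The case against.** The best defence is that this is a small matter that a programmer would notice and settle, and that the bands follow the visit schedule sensibly: 28, 56, 84 and 140 days are the Week 4, 8, 12 and 20 site visits. The second half of that stands. The cut points are reasonable, and one band from Week 12 to Week 20 reflects the absence of a scheduled site visit in between. A reader might infer that putting a patient who stopped at Day 85 in the same band as completers is itself an error. It is a reporting preference. The first half does not remove the point, because neither document says where a duration above 140 days goes.

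A reader might also infer that the trial could not then show dose-related stopping or full exposure by arm. The documents do not support that. SAP 4.3 plans Kaplan-Meier plots of time to end of study treatment by group. SAP 6.1.1 tabulates premature discontinuation of study medication with reasons by group. SAP 6.3.1 summarises duration, time on medication, tablets taken and total amount. SAP 6.3.4 tabulates adverse events leading to withdrawal or interruption. Patients with 141 or 142 days remain in these outputs.

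Finally, a reader might turn two of five in-window days into a share, 2/5 = 40% of completers. That assumes visits spread evenly over the window and every first dose on Day 0 of the count. The documents give no distribution of visit days, so neither this nor any lower share can be defended.

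**Conclusion.** The category list is wrong as written, though the consequence is minor. Compliant completers whose Week 20 visit falls on Day 141 or 142, with the last dose the day before, have 141 or 142 days of treatment and no category. This rests on visit days being counted from the first dose on Day 0. Counting from a planned Day 0 narrows the gap but does not close it.

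The effect is limited to one descriptive exposure table, whose counts by arm need not sum to the safety set. No efficacy analysis, error rate or safety denominator changes. The number of patients affected cannot be derived from the documents.

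**What to change.** Leave the top category open-ended in SAP 6.3.1. Either replace the last band by over 84 days, or keep it and add a band for over 140 days. The first is simpler. The second keeps the existing limits but separates completers only by whether their last visit fell on time or a day or two late.

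A cut at 138 days, meant to isolate completers, is not recommended. If the baseline window shifts the day count, a patient first dosed on Day 2 and seen on Day 138 has 137 - 2 + 1 = 136 days and would be placed among the early stoppers although in window. A single missed final dose before a Day 138 visit would do the same: 136 - 0 + 1 = 137 days.

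The cost is one line in the SAP and one table shell. No new data are needed and no test or study procedure changes.
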